5.3.2.2 Venetoclax Toxicity Management

Prophylaxis and Management of Tumor Lysis Syndrome

Venetoclax can cause rapid reduction in tumor and thus poses a risk for TLS in the Ramp-up Period. Changes in electrolytes consistent with TLS that require prompt management can occur as early as 6-8 hours following the first dose of venetoclax and at each dose increase. The risk of TLS is a continuum based on multiple factors, including comorbidities. Subjects with high tumor burden are at a greater risk of TLS when initiating venetoclax. Reduced renal function further increases the risk. The risk may decrease as tumor burden decreases with venetoclax treatment.

Tumor burden assessments, including radiographic evaluation (eg, CT scan) should be performed at Screening as well as blood chemistry assessments (creatinine, uric acid, potassium, phosphorus, calcium, and albumin, if available) in all subjects. Pre-existing abnormalities should be corrected prior to initiation of treatment with venetoclax.

The prophylaxis measures listed below should be followed and more intensive measures (including hospitalization) should be employed as overall risk increases:

Hydration: Ensure adequate hydration (1.5-2 L) 48 hours prior to initiating therapy with venetoclax and throughout the Ramp-up Period, especially on the first day of each ramp-up dose. Administer intravenous (IV) fluids as indicated based on overall risk of TLS or for those who cannot maintain adequate oral hydration.

Anti-hyperuricemic agents: Administer allopurinol within 72 hours prior to initiation of venetoclax; consider continuing through the Ramp-up Period. Rasburicase is recommended for subjects at high risk, especially those with high tumor burden.

Laboratory Assessments:

Pre-dose: Assess blood chemistries prior to initiating venetoclax to evaluate kidney function and correct pre-existing abnormalities. Reassess blood chemistries before starting each subsequent ramp-up dose of venetoclax.

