- Within the first 24 hours after either the first dose or dose escalation, if any laboratory criteria below are met, the patient should be hospitalized for monitoring and the investigator notified. No additional venetoclax doses should be administered until resolution. A rapidly rising serum potassium is a medical emergency.
- Nephrology (or other acute dialysis service) should be contacted/consulted (per institutional standards to ensure emergency dialysis is available) on admission for any subject hospitalized prophylactically or in response to laboratory changes.
- IV fluids (eg, D5 1/2 normal saline) should be initiated at a rate of at least 1 mL/kg/hr rounded to the nearest 10 mL (target 150 to 200 mL/hr; not < 50 mL/hr). Modification of fluid rate should also be considered for individuals with specific medical needs.
- Monitor for symptoms or signs of TLS (eg, fever, chills, tachycardia, nausea, vomiting, diarrhea, diaphoresis, hypotension, muscle aches, weakness, paresthesias, mental status changes, confusion, seizures). If any clinical features are observed, recheck potassium, phosphorus, uric acid, calcium and creatinine within 1 hour STAT.
- Vital signs should be taken at time of all blood draws or any Intervention.
- The management recommendations below focus on the minimum initial responses required. If a diagnosis of TLS is established, ongoing intensive monitoring and multi-disciplinary management will be per institutional protocols

In addition to the recommendations in the table below:

- For potassium increase ≥ 0.5 mmol/L from baseline, or any value > 5.0 mmol/L, recheck potassium, phosphorus, uric acid, calcium and creatinine within 1 hour STAT and follow first guideline.
- For phosphorus increase of > 0.5 mg/dL AND > 4.5 mg/dL, administer phosphate binder and recheck potassium, phosphorus, uric acid, calcium and creatinine within 1 hour STAT.

Abnormality	Management Recommendations ^{1,2}
Hyperkalemia (including rapidly rising po	otassium)
Potassium ≥ 0.5 mmol/L increase from prior value (even if potassium within normal limits [WNL])	• Recheck potassium, phosphorus, uric acid, calcium and creatinine in 1 hour STAT. If further ≥ 0.2 mmol/L increase in potassium, but still < upper limit of normal (ULN), manage as per potassium ≥ ULN. Otherwise recheck in 1 hour.
	Resume per protocol testing if change in potassium is < 0.2 mmol/L, and potassium < ULN, and no other evidence of tumor lysis.

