	At discretion of Investigator, may recheck prior to hospitalization. If stable or decreased, and still WNL, hospitalization is at the discretion of the Investigator. Potassium, phosphorus, uric acid, calcium and
	Creatinine must be rechecked within 24 hours.
Potassium > upper limit of normal	Perform STAT ECG and commence telemetry.
	Nephrology notification with consideration of initiating dialysis.
	Administer Kayexalate 60 g (or Resonium A 60 g).
	Administer furosemide 20 mg IV × 1.
	Administer calcium gluconate 100 – 200 mg/kg IV slowly if there is ECG/telemetry evidence of life-threatening arrhythmias.
	Recheck potassium, phosphorus, uric acid, calcium and creatinine in 1 hour STAT.
	 If potassium < ULN 1 hour later, repeat potassium, phosphorus, uric acid, calcium and creatinine 1, 2 and 4 hours, if no other evidence of tumor lysis.
Potassium \geq 6.0 mmol/L (6.0 mEq/L)	Perform STAT ECG and commence telemetry.
and/or symptomatic (eg, muscle cramps, weakness, paresthesias, nausea,	Nephrology (or other acute dialysis service) assessment with consideration of initiating dialysis.
vomiting, diarrhea)	Administer Kayexalate 60 g (or Resonium A 60 g).
	Administer furosemide 20 mg IV × 1.
	Administer insulin 0.1 U/kg IV + D25 2 mL/kg IV.
	Administer sodium bicarbonate 1 to 2 mEq/kg IV push.
	If sodium bicarbonate is used, rasburicase should not be used as this may exacerbate calcium phosphate precipitation.
	Administer calcium gluconate 100 to 200 mg/kg IV slowly if there is ECG/telemetry evidence of life-threatening arrhythmias. Do not administer in same IV line as sodium bicarbonate.
	Recheck potassium, phosphorus, uric acid, calcium and creatinine every hour STAT.
Hyperuricemia	
Uric acid ≥ 8.0 mg/dL (476 μmol/L)	Consider rasburicase (0.2 mg/kg as an intravenous infusion over 30 minutes).
	 If rasburicase is used, sodium bicarbonate should not be used as this may exacerbate calcium phosphate precipitation.
	Recheck potassium, phosphorus, uric acid, calcium and creatinine in 1 hour STAT.

Abnormality	Management Recommendations ^{1,2}

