Uric acid \geq 10 mg/dL (595 μ mol/L) OR Uric acid \geq 8.0 mg/dL (476 μ mol/L) with 25% increase and creatinine increase \geq 0.3 mg/dL (\geq 0.027mmol/L) from pre-dose level	 Administer rasburicase (0.2 mg/kg as an intravenous infusion over 30 minutes). When rasburicase is used, sodium bicarbonate should not be used as this may exacerbate calcium phosphate precipitation. Consult nephrology (or other acute dialysis service). Recheck potassium, phosphorus, uric acid, calcium and creatinine in 1 hour STAT. If uric acid < 8.0 mg/dL 1 hour later, repeat potassium, phosphorus, uric acid, calcium and creatinine 2 and 4 hours later, if no other evidence of tumor lysis.
Hypocalcemia	
Calcium ≤ 7.0 mg/dL (1.75 mmol/L) AND Patient symptomatic (eg, muscle cramps, hypotension, tetany, cardiac arrhythmias)	 Administer calcium gluconate 50 to 100 mg/kg IV slowly with ECG monitoring. Telemetry. Recheck potassium, phosphorus, uric acid, calcium and creatinine in 1 hour STAT. If calcium normalized 1 hour later, repeat potassium, phosphorus, uric acid, calcium and creatinine 2 and 4 hours later, if no other evidence of tumor lysis. Calculate corrected calcium and check ionized calcium if albumin low
Hyperphosphatemia	
Phosphorus \geq 5.0 mg/dL (1.615 mmol/L) with \geq 0.5 mg/dL (0.16 mmol/L) increase	 Administer a phosphate binder (e.g., aluminum hydroxide, calcium carbonate, sevelamer hydroxide, or lanthanum carbonate). Nephrology (or other acute dialysis service) notification (dialysis required for phosphorus ≥ 10 mg/dL). Recheck potassium, phosphorus, uric acid, calcium and creatinine in 1 hour STAT. If phosphorus < 5.0 mg/dL 1 hour later, repeat potassium, phosphorus, uric acid, calcium and creatinine 2 and 4 hours later, if no other evidence of tumor lysis.
Creatinine	
Increase ≥ 25% from baseline	 Start or increase rate of IV fluids. Recheck potassium, phosphorus, uric acid, calcium and creatinine in 1 to 2 hours STAT.

Section 2: Ongoing Dosing of Venetoclax

Management of electrolyte changes from last value at intervals > 24 hours after either the first dose or dose escalation (eg, 48 or 72 hours) are as below.

Note: If the patient is hospitalized, no additional venetoclax doses should be administered until resolution.

- FINAL
- For potassium, admit patient for any increase $\geq 1.0 \text{ mmol/L } (1.0 \text{ mEq/L})$, or any level > upper limit of normal.

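### In Appendix H, the potassium row at 6.0 mmol/L or more and the upper uric acid row direct sodium bicarbonate and rasburicase respectively, each advises against the other drug, and nothing says which yields when both rows are met

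*Protocol*

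**What the plan says.** All the key text is in the Section 1 table of Appendix H, on the first venetoclax dose and dose escalation.

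- **Potassium of at least 6.0 mmol/L, and/or symptomatic.** The row directs "Administer sodium bicarbonate 1 to 2 mEq/kg IV push" and then states "If sodium bicarbonate is used, rasburicase should not be used as this may exacerbate calcium phosphate precipitation".
- **Upper uric acid row** (at least 10 mg/dL, or at least 8.0 mg/dL with a 25% increase and a creatinine increase of at least 0.3 mg/dL from the pre-dose level). The row directs "Administer rasburicase (0.2 mg/kg as an intravenous infusion over 30 minutes" and then states "When rasburicase is used, sodium bicarbonate should not be used as this may exacerbate calcium phosphate precipitation".
- **Lower uric acid row** (at least 8.0 mg/dL). The wording is softer: "Consider rasburicase (0.2 mg/kg as an intravenous infusion over 30 minutes".
- **Status of the table.** The introduction says "The management recommendations below focus on the minimum initial responses required". The same bullet leaves ongoing monitoring and multidisciplinary management to institutional protocols once TLS is diagnosed.

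On prophylaxis, Section 5.3.2.2 says "Rasburicase is recommended for subjects at high risk, especially those with high tumor burden", and the screening list in Section 8.1.1 includes prescribing rasburicase for high-risk subjects.

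**The concern.** The table recognises that the two drugs should not be combined and names the hazard, calcium phosphate precipitation. It writes that caution into each row separately and never says what to do when both rows apply. The action line in each row is an unconditional direction, so following one row means departing from the other.

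TLS is an important identified risk of venetoclax, especially in CLL and MCL (Section 1.3.3.1), and the appendix treats a rapidly rising potassium as an emergency. An instruction that staff must first reconcile is hard to use at that moment, and sites may reconcile it differently. That would make subject protection uneven. It could also add site-to-site variation to the TLS management data, which Protocol Section 10.2.3 and SAP Section 1.2 list among the safety endpoints.

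**Working it through.** No figure in the plan needs reproducing. The check sets the rows side by side, looks for a rule of precedence, and asks what can be said about size.

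**Step 1. The rows (Appendix H, Section 1 table).**

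| Row | Sodium bicarbonate | Rasburicase |
|---|---|---|
| Potassium ≥ 6.0 mmol/L and/or symptomatic | directed | not to be used if bicarbonate is used |
| Uric acid ≥ 10 mg/dL, or ≥ 8.0 mg/dL with 25% rise and creatinine rise ≥ 0.3 mg/dL | not to be used when rasburicase is used | directed |
| Uric acid ≥ 8.0 mg/dL | not to be used if rasburicase is used | to be considered |
| Potassium above the upper limit of normal | not mentioned | not mentioned |

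**Step 2. The combinations.**

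- *Potassium ≥ 6.0 row with the upper uric acid row.* The first requires bicarbonate without rasburicase. The second requires rasburicase without bicarbonate. No action satisfies both.
- *Potassium ≥ 6.0 row with the lower uric acid row.* Giving bicarbonate, considering rasburicase and not giving it satisfies both. There is no forced conflict.
- *Lesser potassium row with either uric acid row.* Bicarbonate is not directed, so there is no conflict.

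Only the first pair fails. Section 2 of the appendix sends later potassium and uric acid changes back to the same table, so that pair can recur after the first 24 hours.

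**Step 3. Is there a rule of precedence?** None appears in the Appendix H introduction, either row, Section 2 of the appendix, Section 5.3.2.2, Section 7.1.1.10 or Section 8.1.1. Section 3.1.1 refers TLS events in the run-in to standard institutional practice, without saying which initial drug instruction gives way.

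**Step 4. Can the two triggers coincide?** Appendix G counts potassium above 6.0 mmol/L and uric acid above 8.0 mg/dL as two of four laboratory TLS abnormalities, and two within 24 hours suffice. A subject with that pair who also has a 25% uric acid rise and a creatinine rise of 0.3 mg/dL meets both directing rows. So does one whose uric acid reaches 10 mg/dL. The overlap is plausible; its frequency is not given.

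**Step 5. Size.** Planned venetoclax recipients: 27 run-in + 260/2 = 130 randomized + 75 treatment-naive = 232. Section 1.3.2.2 reports laboratory TLS in 1.5% to 2.5% of subjects across three NHL studies. If those rates carried over:

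- 232 × 0.015 = 3.5
- 232 × 0.025 = 5.8

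These are all laboratory TLS events, not subjects meeting both rows. The share meeting both is not in the documents. Nor is the range a strict ceiling, because the potassium row can also be read as triggered by symptoms without a value of 6.0 mmol/L.

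**The case against.** The strongest reply is that the appendix is guidance. Its title and column heading speak of recommendations, the cautions say the other drug should not be used, and the potassium row's caution is conditional, which suggests that bicarbonate may not always be given. Both rows bring in nephrology or a dialysis service, institutional protocols govern once TLS is diagnosed, and most steps in each row can still be carried out.

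Much of this stands. It rules out saying that the two instructions are mandatory in a strict sense or that such a subject cannot be managed. It does not remove the conflict. The introduction calls the entries the minimum initial responses, the authors used softer wording in the lower uric acid row when they meant a step to be optional, and the institutional clause in Appendix H concerns ongoing management after diagnosis.

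Three stronger readings are tempting and are not supported:

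- *Any subject with the potassium and uric acid criteria of Appendix G is caught.* That criterion is uric acid above 8.0 mg/dL, where Appendix H only asks that rasburicase be considered.
- *Prophylactic rasburicase makes the potassium row contradictory by itself.* The cautions against bicarbonate sit in the hyperuricemia rows, and the prophylaxis text states neither a bar nor an interval. This is a sequence left unaddressed, not a stated contradiction.
- *Up to 19 subjects are affected* (232 × 2/24 = 19.3, from the AIM study in Section 1.4.7). That counts all TLS. Section 1.4.2 places both AIM events under a 50 mg start that was then lowered to 20 mg, with no TLS in the next 8 subjects; this trial starts at 20 mg.

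**Conclusion.** The two rows contradict each other as written for a subject who meets both, and no text resolves it. This is an internal inconsistency in a safety instruction, confined to one pair of rows. It rests on reading the two action lines as directions, which their wording and the introduction support.

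The number of subjects affected cannot be derived and is likely to be small. In the NHL studies that supply the 1.5% to 2.5% rates, all TLS cases resolved and none was clinical TLS. No hypothesis test is affected, since Protocol Section 10.6 plans no formal testing of safety data. Much of the ramp-up is probably past: SAP Section 1 says that the treatment-naive cohort has completed enrollment, and SAP Section 4 already reports a count by randomization stratum. The text still matters for subjects who repeat ramp-up levels after a dosing interruption (Section 5.3.2.5). The point merits correction because the hazard is one the protocol itself names.

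**What to change.** The sponsor's clinical team should reconcile the potassium ≥ 6.0 mmol/L row with the upper uric acid row, and print the same instruction in both for a subject who meets both. At the same time they should state whether rasburicase given earlier as prophylaxis under Sections 5.3.2.2 and 8.1.1 counts as used when the potassium row is reached. Which agent takes priority is a clinical decision, and no view is offered here. The lower uric acid row needs only a check that it stays consistent with the result.

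The cost is a sentence or so in Appendix H, by clarification letter or with the next amendment. It needs no extra visits, subjects or analyses.

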Appendix I. FACT-Lym questionnaire (version 4)

(http://www.facit.org/FACITOrg/Questionnaires)

Below is a list of statements that other people with your illness have said are important. Please circle or mark one number per line to indicate your response as it applies to the past 7 days.

	PHYSICAL WELL-BEING	Not at all	A little bit	Some -what	Quite a bit	Very much
GP1	I have a lack of energy	0	1	2	3	4
GP2	I have nausea	0	1	2	3	4
GP3	Because of my physical condition, I have trouble meeting the needs of my family	0	1	2	3	4
GP4	I have pain	0	1	2	3	4
GP5	I am bothered by side effects of treatment	0	1	2	3	4
GP6	I feel ill	0	1	2	3	4
GP7	I am forced to spend time in bed	0	1	2	3	4
	SOCIAL/FAMILY WELL-BEING	Not at all	A little bit	Some -what	Quite a bit	Very much
GS1	I feel close to my friends	0	1	2	3	4
GS2	I get emotional support from my family	0	1	2	3	4
GS3	I get support from my friends	0	1	2	3	4
GS4	My family has accepted my illness	0	1	2	3	4
GS5	I am satisfied with family communication about my illness	0	1	2	3	4

GS6	I feel close to my partner (or the person who is my main support)	0	1	2	3	4
Q1	Regardless of your current level of sexual activity, please answer the following question. If you prefer not to answer it, please mark this box and go to the next section.					
GS7	I am satisfied with my sex life	0	1	2	3	4
Please	circle or mark one number per line to indicate you	r resnon	ise as it a	nnlies to	the nast	7 days

Please circle or mark one number per line to indicate your response as it applies to the past 7 days.

	EMOTIONAL WELL-BEING	Not at all	A little bit	Some- what	Quite a bit	Very much
GE1	I feel sad	0	1	2	3	4
GE2	I am satisfied with how I am coping with my illness	0	1	2	3	4
GE3	I am losing hope in the fight against my illness	0	1	2	3	4
GE4	I feel nervous	0	1	2	3	4
GE5	I worry about dying	0	1	2	3	4
GE6	I worry that my condition will get worse	0	1	2	3	4
	FUNCTIONAL WELL-BEING	Not at all	A little bit	Some- what	Quite a bit	Very much
GF1	I am able to work (include work at home)	0	1	2	3	4
GF2	My work (include work at home) is fulfilling	0	1	2	3	4

IMBRUVICA® (ibrutinib) PCYC		C-1143-CA Amendment 4			16 Septem	iber 2022 FINAL
GF3	I am able to enjoy life	0	1	2	3	4
GF4	I have accepted my illness	0	1	2	3	4
GF5	I am sleeping well	0	1	2	3	4
GF6	I am enjoying the things I usually	do for fun 0	1	2	3	4

I am content with the quality of my life right 0 1 2 3 4

GF7

Please circle or mark one number per line to indicate your response as it applies to the past 7 days.

	ADDITIONAL CONCERNS	Not at all	A little bit	Some -what	Quite a bit	Very much
P2	I have certain parts of my body where I experience pain	0	1	2	3	4
LEU1	I am bothered by lumps or swelling in certain parts of my body (e.g., neck, armpits, or groin)	0	1	2	3	4
BRM3	I am bothered by fevers (episodes of high body temperature)	0	1	2	3	4
ES3	I have night sweats	0	1	2	3	4
LYM1	I am bothered by itching	0	1	2	3	4
LYM2	I have trouble sleeping at night	0	1	2	3	4
ВМТ6	I get tired easily	0	1	2	3	4
C2	I am losing weight	0	1	2	3	4
Ga1	I have a loss of appetite	0	1	2	3	4
HI8	I have trouble concentrating	0	1	2	3	4
N3	I worry about getting infections	0	1	2	3	4
LEU6	I worry that I might get new symptoms of my illness	0	1	2	3	4
LEU7	I feel isolated from others because of my illness or treatment	0	1	2	3	4
BRM9	I have emotional ups and downs	0	1	2	3	4
LEU4	Because of my illness, I have difficulty planning for the future	0	1	2	3	4

Appendix J. EQ-5D-5L

(English version for the UK)

UK (English) v. 2 \otimes 2009 EuroQol Group. EQ-5D $^{\intercal M}$ is a trade mark of the EuroQol Group

Under each heading, please tick the ONE box that best describes your health TODAY

[figure not shown]
MOBILITY I have no problems in walking about I have slight problems in walking about I have moderate problems in walking about	
I have severe problems in walking about I am unable to walk about	
SELF-CARE I have no problems washing or dressing myself I have slight problems washing or dressing myself I have moderate problems washing or dressing myself I have severe problems washing or dressing myself I am unable to wash or dress myself	
USUAL ACTIVITIES (e.g. work, study, housework, family or leisure activities) I have no problems doing my usual activities I have slight problems doing my usual activities I have moderate problems doing my usual activities I have severe problems doing my usual activities I am unable to do my usual activities	
PAIN / DISCOMFORT I have no pain or discomfort I have slight pain or discomfort I have moderate pain or discomfort I have severe pain or discomfort I have extreme pain or discomfort	
ANXIETY / DEPRESSION I am not anxious or depressed I am slightly anxious or depressed I am moderately anxious or depressed I am severely anxious or depressed I am extremely anxious or depressed	

 $\label{eq:local_problem} \text{UK (English) v.2 @ 2009 EuroQol Group. EQ-5D^{\text{TM}} is a trade mark of the EuroQol Group}$

. We would like to know how good or bad your health is TODAY.

- This scale is numbered from 0 to 100.
- 100 means the best health you can imagine. 0 means the $\underline{\text{worst}}$ health you can imagine.
- Mark an X on the scale to indicate how your health is TODAY.
- . Now, please write the number you marked on the scale in the box below.

YOUR HEALTH TODAY =

The best health you can imagine

you can imagine

3
UK (English) v.2 © 2009 EuroQol Group. EQ-5D™ is a trade mark of the EuroQol Group

PT Preferred Term
QoL Quality of life

RDI Relative Dose Intensity
R/R Relapsed/Refractory
SAE Serious Adverse Event
SAP Statistical Analysis Plan
SCT Stem Cell Transplant

SD Stable Disease

SMQ Standardized MedDRA query

SOC System Organ Class

SRC Safety Review Committee

SRI Safety Run-in

TEAE Treatment-Emergent Adverse Event

TLS Tumor Lysis Syndrome

TN Treatment Naive

TTNT Time to Next Treatment

Page 7 of 35

1 INTRODUCTION

This statistical analysis plan (SAP) is based on Protocol Amendment 4 dated September 25, 2022 and defines key elements including variable definitions and statistical methods for analysis of data in evaluation of efficacy and safety for subjects with the Relapsed/Refractory (R/R) mantle cell lymphoma (MCL) who are enrolled in the study PCYC-1143-CA.

Study PCYC-1143-CA also contains a separate arm treatment-naïve (TN) MCL cohort which has completed enrollment; an SAP addendum will be provided for the treatment-naïve (TN) MCL cohort at the appropriate time prior to the primary analysis. Subject demographics and disease characteristics and relevant safety data will be summarized for subjects with TN MCL who are enrolled at the time of the primary analysis for the subjects with R/R MCL.

The analyses of exploratory biomarkers and pharmacokinetics (PK) data are not in the scope of this document. Throughout this SAP, "study treatment" and "study drug" are used interchangeably, and both are referring to ibrutinib and venetoclax or placebo.

Analysis methods specified in this document take precedence over those described in the protocol, should there be any differences. Any changes in the protocol will be documented in Section 7, Changes in the Protocol Planned Analysis. This SAP will be finalized before unblinding of the study results.

